### Infants:

This is an as-treated analysis including only the infants born to women who have been vaccinated and those who have received the PCV-10 vaccination prior to the week 8 study visit.

Summaries will include the proportion (%) and 95% CI of infants born to mothers who received PCV-10 or PPV-23 vaccines who had ELISA-measured IgG PNC antibody levels  $\geq 0.35\mu\text{g/mL}$  at 8 weeks of age for  $\geq 1$  serotype listed above. The difference in proportions between the two groups will be assessed using a Chi-Square test.

In the case of twins, one child will be chosen at random for the primary immunogenicity analysis. Sensitivity analyses will repeat these summaries in the event that twins are enrolled in the study, re-doing the analysis using the other sibling.

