## 3 Protocol Overview

### 3.1 Study Design

**DESIGN:** A double-blind, randomized, placebo-controlled study to evaluate the safety and immunogenicity of two pneumococcal vaccines in HIV-infected pregnant women in their second or third trimester on highly active antiretroviral therapy (HAART) and their infants.

**SAMPLE SIZE:** Approximately 345 Human Immunodeficiency Virus (HIV)-infected pregnant women and their 345 infants (690 participants), equally distributed among three treatment arms to obtain  $\geq 100$  evaluable pairs/arm (300 total pairs, or 600 total participants).

**REGIMEN:** **Step 1.** Pregnant women will be randomized between  $\geq 14$  weeks (14 weeks 0 days) to  $< 33$  weeks (32 weeks 6 days) of gestation to one of three blinded treatment arms (administered on Day 0):

- Arm 1A: pneumococcal polysaccharide 23-valent vaccine (PPV-23);
- Arm 1B: pneumococcal conjugate 10-valent vaccine (PCV-10); or
- Arm 1C: placebo.

**Step 2.** Women randomized to Arm 1C (placebo) who complete Step 1 will be screened for entry into Step 2 and will be randomized to receive PPV-23 (Arm 2A) or PCV-10 (Arm 2B) at 24 weeks after delivery. The women who received active vaccine during pregnancy (Arms 1A and 1B) will stop study at 24 weeks after delivery.

**Step 3.** Women who were initially randomized to Arm 1C and meet an exclusion criterion for Step 2 due to new pregnancy will be enrolled in Step 3 and receive open label PCV-10 at the last study visit (which coincides with Step 1 24 weeks post-delivery).

All infants will receive PCV-10 per local standard of care.

STUDY DURATION: Up to 60 weeks for women (approximately 28 weeks pre-delivery; 32 weeks post-delivery) and up to 28 weeks for infants.

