#### Neonatal:

- Grade  $\geq 3$  AEs
- Congenital defects

- HIV infections
- Pneumonia or IPD

2. To compare the immunogenicity of PCV-10 with PPV-23 vaccines in HIV-infected pregnant women on HAART.
  - Outcome measure:
    - Raw values and fold change in ELISA-measured IgG PNC antibody concentrations from baseline to week 4 in Step 1 to  $\geq 1$  serotype. Serotypes measured by ELISA are: 1, 4, 5, 6B, 7F, 14, 23F and 33F.
3. To compare the level of Pneumococcal (PNC) antibodies at 8 weeks of life in infants born to mothers who received PCV-10 or PPV-23 vaccines.
  - Outcome measures:
    - ELISA-measured IgG PNC antibody levels  $\geq 0.35\text{ug/mL}$  at 8 weeks of age for  $\geq 1$  serotype from those listed above.

Secondary objectives and outcome measures:

1. To compare the level of transplacentally transferred vaccine-serotype PNC antibodies in infants born to mothers who received PCV-10 or PPV-23 versus placebo.
  - Outcome measure: Average ratio of infant/mother ELISA-measured IgG PNC antibody levels across the serotypes listed above, measured at birth/delivery
2. To compare the immunogenicity of PCV-10 and PPV-23 vaccines with placebo in HIV-infected pregnant women on HAART.
  - Outcome measure: ELISA-measured IgG PNC antibody concentrations at week 4 in Step 1, in all treatment groups
3. To compare the persistence of vaccine-serotype PNC anti-capsular antibodies for up to 24 weeks after delivery in HIV-infected women vaccinated with PCV-10, PPV-23 or placebo.
  - Outcome measure: ELISA-measured IgG PNC antibody concentrations at labor&delivery and week 24 post-delivery in Step 1, in all treatment groups
4. To compare maternal antibody responses to PPV-23 or PCV-10 administered during pregnancy with responses to PPV-23 or PCV-10 administered 24 weeks postpartum.
  - Outcome measure: ELISA-measured IgG PNC antibody concentrations at week 4 in

Step 1 and at week 4 in Step 2, in the women who received PPV-23 or PCV-10

5. To evaluate the effect of the following factors on the magnitude and persistence of the maternal antibody responses to PCV-10 and PPV-23: maternal age, ethnicity, cluster of differentiation 4 (CD4), cluster of differentiation 8 (CD8), plasma HIV RNA and gestational age at immunization.
  - Outcome measure: ELISA-measured IgG PNC antibody concentrations at week 4 in Step 1, in the women who received PPV-23 or PCV-10, and the following variables (measured at week 0):
    - maternal age,
    - ethnicity,

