### **4.2 Analysis Populations**

Any mother participants found to be ineligible and who the study team determine should not be included in any analyses, will be included in accrual and eligibility summaries only. Protocol deviations will be summarized but should not result in any participants being excluded from analyses.

Safety population: Safety analyses will be as-treated and include all women who received study vaccination and all infants who were born alive.

Immunogenicity population: The primary immunogenicity analyses will use an as-treated approach, limited to women who received study vaccination and all infants who were born alive. In addition, the primary immunogenicity analysis in infants will be restricted to those who did not receive the PCV-10 vaccination prior to the week 8 evaluation. If more than one child is born to a pregnant woman, one child will be randomly selected to be included in the primary immunogenicity analyses.

For the immunogenicity analysis in secondary objective #6, infants who did not receive the PCV-10 vaccinations within the correct windows will be excluded. The windows are described below in section 5.1.

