## 5 Statistical Methods

Baseline characteristics will be summarized by treatment group but with no statistical comparisons comparing arms.

Statistical tests will not be adjusted for interim monitoring or multiple comparisons. The Chi-square tests will be used to compare rates of response following vaccination between the vaccinated groups and placebo group. The statistical tests will be two-sided with a nominal significance level of 0.05. Categorical data will be summarized using N (%) and 90% or 95% confidence intervals (CIs), and continuous data using N, min, Q1, median, Q3, max, and mean (STD) (when appropriate) and 95% CI.

Any modifications to outcome measures after the team has seen data collected after entry will be identified as *post hoc* in the analysis report.

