#### Infant Schedule:

Study visits for infants were conducted at birth (with a window of +7 days), week 8, which should be  $\leq 7$  days before the 1st dose of PCV-10 (with a window of +14 days), week 16, which should be  $\leq 7$  days before the 2nd dose of PCV-10 (with a window of  $\pm 28$  days), week 24, which

should be  $\geq$  28 days after the 2nd dose of PCV-10 (with a window of 28 days), or for Invasive Pneumococcal Disease (IPD).

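### SAP Section 5.3 reverses the infant PCV-10 restriction of Section 4.2, so the infant primary immunogenicity analysis, as written there, uses the wrong infants

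*SAP*

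**What the plan says.** Two sections of the SAP define the infant population for primary objective 3.

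- **Section 4.2 (Analysis Populations)** starts from infants born alive and adds that the primary infant immunogenicity analysis "will be restricted to those who did not receive the PCV-10 vaccination prior to the week 8 evaluation".
- **Section 5.3 (Infants)**, which also specifies the proportion, its 95% CI and the Chi-square test, limits the as-treated analysis to infants of vaccinated women and "those who have received the PCV-10 vaccination prior to the week 8 study visit".

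Three other places bear on which rule is meant.

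- **Section 5.1 (Infant Schedule)** puts the week 8 visit no more than 7 "days before the 1 st dose of PCV-10 (with a window of +14 days").
- **Section 3.2, primary objective 3** compares antibody "at 8 weeks of life in infants born to mothers who received PCV-10 or PPV-23 vaccines".
- **Section 3.1** states: "All infants will receive PCV-10 per local standard of care".

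**The concern.** One section excludes infants who had their own PCV-10 before the week 8 sample. The other makes that early dose a condition of entry. This is a primary analysis, and the inverted rule sits in the section that describes its estimate and test.

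The objective concerns what the infant carries at 8 weeks as a result of the mother's vaccine. An infant already dosed with PCV-10 may have antibody from that dose. Because infants in both compared groups receive PCV-10, their own response could raise the proportion above 0.35 µg/mL in both groups and blur the maternal comparison. The infants admitted by Section 5.3 would also be those vaccinated off schedule, who may be few and may differ from the rest. The twin sensitivity analysis in Section 5.3 repeats the same summaries, so it would inherit the same population.

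**Working it through.** The SAP gives no power, effect size or response rate for this analysis, so there is no figure to reproduce. The check is a comparison of text, followed by an illustration of scale.

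**1. The two rules side by side**

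| Infant's status at week 8 | Section 4.2 | Section 5.3 (both conditions required) |
|---|---|---|
| No PCV-10 yet | in | out |
| PCV-10 already given | out | in |

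On this condition the rules are complements and their overlap is empty.

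**2. Which rule fits the rest of the SAP**

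Under Section 5.1 an on-schedule infant is seen at week 8 before dose 1. That infant is in under Section 4.2 and out under Section 5.3. Objective 3 calls for a measurement that the infant's own vaccine has not influenced, which again is Section 4.2. The schedule, the objective and the population section agree; Section 5.3 stands alone.

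**3. The other possible reading of Section 5.3**

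The words *and those* could be read as a union: infants of vaccinated women, plus infants dosed early. No on-schedule infant of a vaccinated woman is then lost. But the early-dosed infants stay in, and they are the ones Section 4.2 removes. Neither reading gives the Section 4.2 population.

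**4. Scale under the joint reading (illustration)**

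Inputs:
- 100 evaluable pairs per arm (Section 3.1), taken here as 100 infants per arm with a week 8 result.
- Share dosed before week 8: not in the SAP; assumed at 2%, 5%, 10% and 20%.
- Worst-case 95% half-width for a proportion: 1.96 × √(0.25/n).

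Infants kept per arm are 100 × share under Section 5.3 and 100 × (1 − share) under Section 4.2.

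| Assumed share | n, Section 5.3 | Half-width | n, Section 4.2 | Half-width |
|---|---|---|---|---|
| 2% | 2 | not meaningful | 98 | 9.9 points |
| 5% | 5 | 44 points | 95 | 10.1 points |
| 10% | 10 | 31 points | 90 | 10.3 points |
| 20% | 20 | 22 points | 80 | 11.0 points |

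For example, 1.96 × √(0.25/10) = 0.310 and 1.96 × √(0.25/90) = 0.103. With all 100 infants the half-width would be 0.098. The normal approximation is rough at the smallest sizes, so those entries show order of magnitude only.

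**The case against.** The best defence is that the intent is plain. Section 4.2 is the section devoted to populations, it states the sensible rule outright, and nothing gives Section 5.3 precedence over it. A dropped *not* is the likely cause, and a programmer who applied Section 5.3 literally would lose nearly all on-schedule infants and probably notice. Section 1 leaves coding descriptions to the AIP, which is not at hand and may already follow Section 4.2.

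That lowers the chance that the wrong analysis is run, but it does not make the text right. Section 1 says the SAP is to record agreement between team and statistician on the analyses, and two opposite primary populations cannot do that. The AIP could equally have carried the error over.

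Three further points stand as limits on the size of the problem:
- The loss of precision arises only under the joint reading; under the union reading the defect is failure to exclude early-dosed infants.
- The early-vaccination shares are assumed.
- How far the infant's own dose would affect the week 8 result depends on how long before the visit it was given, which the SAP does not say. Contamination is a risk, not a certainty.

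**Conclusion.** The concern holds. Section 5.3 states the inclusion rule for a primary analysis the wrong way round. This follows from the text of Sections 3.2, 4.2, 5.1 and 5.3 and rests on no calculation.

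Its practical size depends on the unknown share of infants dosed before week 8. Within the assumed range, literal use of Section 5.3 would discard between 80 and 98 of every 100 evaluable infants per arm and analyse the remainder, for whom the comparison is least interpretable. It must be corrected because, as the SAP stands, a reader cannot establish which infant population was prespecified.

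**What to change.** In Section 5.3 (Infants), insert *not* so that the analysis includes only infants of vaccinated women who have *not* received PCV-10 before the week 8 visit. Preferably replace the restatement with a reference to the population in Section 4.2, so that the rule stands in one place and the live-birth condition comes with it. Record the change in Sections 2 and 9 of the SAP.

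Then check that the AIP, the analysis programs and the twin sensitivity analysis apply the Section 4.2 condition. If results have already been produced, confirm which population they used, and report how many infants in each arm were excluded for PCV-10 before week 8.

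The cost is one word in the SAP and a short program check. Neither the design nor the data collection changes.

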## 5.4 Secondary Objectives

Summaries will include:

- i) means (or medians if data are not normally distributed) and 95% CI of mean ratio of infant/mother ELISA-measured IgG PNC antibody levels across the serotypes listed above, measured at birth/delivery;
- ii) Summary table with proportion (%) and 95% CI of women in the each treatment group who had a  $\geq$ two-fold increase to each serotypes in ELISA-measured IgG PNC antibody concentrations from baseline to week 4 after immunization in Step 1;
- iii) Summary table with proportion (%) and 95% CI of women by treatment arm who had ELISA-measured IgG PNC antibody levels  $\geq 0.35\text{ug/mL}$  at week 4 after immunization in Step 1, at labor&delivery, and at week 24 post-delivery in Step 1 to  $\geq 1$  of the serotypes listed above;
- iv) Summary table with proportion (%) and 95% CI of women who had a two-fold increase to  $\geq 1$  serotype in ELISA-measured IgG PNC antibody concentrations from baseline to week 4 after immunization in Step 1 vs the women who achieved this from entry to Step 2 until week 4 post immunization in Step 2 (for each of the two vaccines). The analyses will exclude the women who delivered prior to week 4 in Step 1;
- v) Correlations between ELISA-measured IgG PNC antibody concentrations at weeks 4 in Step 1, in the women who received PPV-23 or PCV-10, and the following variables (measured at week 0): maternal age, ethnicity, cluster of differentiation 4 (CD4) count, cluster of differentiation 8 (CD8) count, plasma HIV RNA and gestational age;
- vi) Summary table with proportion (%) and 95% CI of infants born to mothers who received PCV-10 or PPV-23 vaccines who had ELISA-measured IgG PNC antibody levels  $\geq 0.35\text{ug/mL}$  at 16 and 24 weeks of age for  $\geq 1$  serotypes listed above;
- vii) Summary table with mean (95% CI) number of serotypes with levels  $\geq 0.35\text{ug/mL}$  at weeks 16 and 24 of age in study infants.

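### The only planned summary for maternal antibody persistence (secondary objective 3) is an any-of-8-serotypes proportion at 0.35 ug/mL, which is insensitive to waning and leaves the stated concentration outcome without an analysis

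*SAP*

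**What the plan says.** SAP section 3.2, secondary objective 3, reads: "To compare the persistence of vaccine-serotype PNC anti-capsular antibodies for up to 24 weeks after delivery in HIV-infected women vaccinated with PCV-10, PPV-23 or placebo". The outcome measure under it is continuous: "ELISA-measured IgG PNC antibody concentrations at labor&delivery and week 24 post-delivery in Step 1, in all treatment groups".

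The corresponding entry in section 5.4 is item iii. It is a table, by treatment arm, of the proportion (with 95% CI) of women at or above 0.35 ug/mL "at week 4 after immunization in Step 1, at labor&delivery, and at week 24 post-delivery in Step 1 to" at least one "of the serotypes listed above". Section 3.2 gives the list: "Serotypes measured by ELISA are: 1, 4, 5, 6B, 7F, 14, 23F and 33F", which is eight serotypes. Item iii has no week 0 column, no result by serotype, no count of serotypes and no change within a woman.

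The other items of section 5.4 do not fill the gap:

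- Item i uses maternal levels at delivery, but only as the denominator of the infant/mother ratio.
- Item ii is by serotype but stops at week 4: it counts a two-fold "increase to each serotypes in ELISA-measured IgG PNC antibody concentrations from baseline to week 4 after immunization in Step 1".
- Items iv and v concern week 4 responses.
- Item vi is an infant summary.
- Item vii counts serotypes above the threshold, but "at weeks 16 and 24 of age in study infants".

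**The concern.** There are two problems, and the first needs no assumption. Section 3.2 defines the outcome as concentrations, while section 5.4 specifies only a dichotomy of them for the visits that matter.

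The second is the choice of dichotomy. An absolute threshold combined with an any-of-8 rule ignores where the woman started and where she peaked. A woman already above 0.35 ug/mL to one serotype before vaccination can count at each visit, in the placebo arm as well. A different serotype may qualify her at each visit. A fall from, say, 5 to 0.4 ug/mL in one serotype leaves her status unchanged, as does complete loss of antibody to seven serotypes while the eighth stays above the line.

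At stake is the PCV-10 versus PPV-23 comparison after delivery. If background antibody is common, all three arms may show proportions near 100% at all three visits even when residual antibody differs between the vaccines. The post-delivery follow-up would then say little about the persistence it was meant to measure.

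**Working it through.** The SAP gives no background rate, expected decline or power for objective 3, so there is no figure of its own to reproduce.

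**Inputs from the SAP:** 8 serotypes (section 3.2); threshold 0.35 ug/mL and at least one serotype (section 5.4 item iii); two-sided 0.05 (section 5); at least 100 evaluable pairs per arm (section 3.1).

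**Assumptions, not in the SAP:** per-serotype background rate p at 0.35 ug/mL; equal correlation rho between serotypes on the log scale; lognormal concentrations with log10 SD 0.45; residual levels two-fold and four-fold above background.

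**Step 1. Any-of-8 rate from background alone.** With independent serotypes the rate is 1 - (1 - p)^8:

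- p = 0.10: 1 - 0.90^8 = 57%
- p = 0.30: 1 - 0.70^8 = 94%
- p = 0.50: 1 - 0.50^8 = 99.6%

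Independence gives the highest figures. Simulation from an equicorrelated normal model gives:

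| p | independent | rho 0.3 | rho 0.5 | rho 0.7 |
|---|---|---|---|---|
| 0.10 | 57% | 45% | 37% | 29% |
| 0.30 | 94% | 81% | 72% | 61% |
| 0.50 | 99.6% | 95% | 89% | 81% |

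**Step 2. Ability to show a difference in residual antibody.** Suppose that at one visit one vaccine arm is four-fold above background and the other two-fold. With rho 0.5 and 100 women per arm, the any-of-8 proportions and the power of a two-sided 0.05 comparison of the two vaccine arms are:

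| Per-serotype background | Placebo | Two-fold arm | Four-fold arm | Power |
|---|---|---|---|---|
| 11% | 40.0% | 71.2% | 91.6% | 0.96 |
| 29% | 71.1% | 91.6% | 98.7% | 0.64 |
| 50% | 88.8% | 98.0% | 99.8% | 0.23 |
| 70% | 96.9% | 99.7% | 100% | 0.07 |

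Other correlations shift these figures. At 50% background the power is 0.09 with rho 0.3 and 0.44 with rho 0.7.

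**Step 3. The same contrast on the stated outcome.** Four-fold against two-fold is a ratio of geometric means of 2, or log10(2) = 0.301. For one serotype the standard error is 0.45 x sqrt(2/100) = 0.0636. The standardised difference is 0.301/0.0636 = 4.73, and power is Phi(4.73 - 1.96) = Phi(2.77), about 0.997. This does not depend on the background rate. The loss of power in step 2 therefore comes from the summary measure and not from the sample size.

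**The case against.** The strongest reply is that the insensitivity is conditional. At about 11% background the any-of-8 proportion separates the two arms with power of about 0.96, and correlated serotypes pull the background rates well below the independent figures. A reader might infer from item iii that waning cannot be seen, or that the follow-up gives no answer on persistence. The SAP does not support either: it gives no background rate, and concentrations are still measured.

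The randomised placebo arm is in the same table. It would show a ceiling, and arms can be compared at a visit without each woman's baseline. This stands as protection against misreading a ceiling as persistence. It does not recover the comparison between the vaccines once both are at the ceiling.

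It can also be said that section 1 and section 6 leave table detail to the Analysis Implementation Plan, which is not at hand, that section 5 has a general rule for summarising continuous data, and that the list in section 5.4 need not be exhaustive. So one cannot say that no concentration table will ever be produced. But none of these ties concentrations to objective 3, whereas item iii explicitly specifies a proportion.

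Finally, staying above a threshold is a legitimate meaning of persistence, and by that meaning a fall from 5 to 0.4 ug/mL is no loss. That is fair for a single serotype. The weak part is the at-least-one rule, together with the missing baseline.

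**Conclusion.** The point holds as a mismatch and an insensitivity. Section 3.2 names concentrations for objective 3; section 5.4 plans only an any-of-8 threshold proportion for maternal levels over delivery and week 24 post-delivery. That much is read directly from the SAP.

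The size rests on assumptions about background rate, correlation and spread. Under those used here, the loss is small at about 10% per-serotype background, appreciable at about 30%, and severe at 50% or more. The supportable conclusion is that waning may be missed and that the arms may sit near the ceiling, not that they must. Because this is a secondary objective and the remedy is cheap, the change should be made, but the primary analyses are not affected.

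**What to change.** In section 5.4, for objective 3, specify:

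1. The geometric mean concentration by serotype and arm at week 0, week 4, delivery and week 24 post-delivery, with between-arm ratios and 95% CIs at the visits after vaccination. Week 0 can be shown without a test, in line with section 5.
2. The within-woman ratio of week 24 post-delivery to week 0 and to week 4, and of delivery to week 4. Leave women who delivered before week 4 out of the ratios to week 4; item iv already expects such women. Note that time from vaccination to delivery varies, because randomisation runs from 14 to under 33 weeks of gestation.
3. The share at or above 0.35 ug/mL by serotype, with the week 0 share beside it.
4. The existing at-least-one-serotype row, kept as supplementary.

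The cost is SAP wording and more tables. No new samples are needed: item ii already requires week 0 and week 4 values in each arm, and objective 3 already names the two later visits. The downside is many unadjusted comparisons. The geometric means alone give 8 serotypes x 3 visits x 3 arm pairs = 72 ratios, so these results should be labelled descriptive.

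### The pregnancy-versus-postpartum comparison conditions only the postpartum side on completing Step 1, passing Step 2 screening and having no new pregnancy, so it can be biased in an unknown direction

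*SAP*

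**What the plan says.** Secondary objective 4 (SAP section 3.2) is "To compare maternal antibody responses to PPV-23 or PCV-10 administered during pregnancy with responses to PPV-23 or PCV-10 administered 24 weeks postpartum". Item iv of section 5.4 is the only listed summary that serves it. It tabulates, per vaccine, the proportion with a two-fold rise to at least one serotype by week 4 in Step 1, "vs the women who achieved this from entry to Step 2 until week 4 post immunization in Step 2". Its one stated restriction is: "The analyses will exclude the women who delivered prior to week 4 in Step 1".

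Section 3.1 fixes who can be on the postpartum side:

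- "Women randomized to Arm 1C (placebo) who complete Step 1 will be screened for entry into Step 2".
- Those admitted "will be randomized to receive PPV-23 (Arm 2A) or PCV-10 (Arm 2B) at 24 weeks after delivery".
- Arm 1C women who "meet an exclusion criterion for Step 2 due to new pregnancy will be enrolled in Step 3" get open-label vaccine at their last study visit, so no later response is planned for them.

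Arms 1A and 1B are also followed to 24 weeks after delivery, and item iii of section 5.4 already reports antibody levels at that visit by treatment arm. Section 4.2 defines the women's immunogenicity population as those vaccinated, for the primary analyses; it sets no population for the Step 1 versus Step 2 comparison.

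**The concern.** Within each vaccine, item iv contrasts groups that Step 1 randomisation made comparable: Arm 1A with part of Arm 1C for PPV-23, and Arm 1B with the rest of Arm 1C for PCV-10. That protection is weakened when one side is conditioned on events after randomisation and the other is not. A woman in Arm 1A or 1B who gives a week 4 sample and later drops out, dies or becomes pregnant again still counts. An Arm 1C woman with the same later course is absent.

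If such women respond differently from the rest, part of the observed difference reflects who is left in Step 2 and not the timing of vaccination. The early-delivery exclusion addresses neither retention nor new pregnancy. Nor does the SAP say whether it reaches Arm 1C women entering Step 2; if it does not, it is a second one-sided selection.

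**Working it through.** **The SAP's own figures.** Section 3.1 plans 345 women in three equal arms: 345 / 3 = 115 per arm. With their infants, 345 × 2 = 690, as stated. The target of 300 evaluable pairs implies a loss of 1 − 300/345 = 13.0%. No sample size, power or effect size is given for item iv, so there is no figure to reproduce for this comparison.

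**The two sides set next to each other.**

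| Condition | Arms 1A/1B in item iv | Arm 1C in item iv |
|---|---|---|
| Week 4 sample after the vaccination being assessed | yes | yes |
| Not delivered before week 4 of Step 1 | yes | not clear |
| Completed Step 1 to 24 weeks after delivery | not required | required |
| Passed Step 2 screening | not required | required |
| Not newly pregnant | not required | required |

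**Size of the possible bias.** Let s be the share of women who would enter Step 2, p_s their response rate, and g the gap between them and the women who would not enter. With no true timing effect:

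- Postpartum side: p_s
- Pregnancy side: s·p_s + (1 − s)(p_s − g)
- Spurious difference: (1 − s)·g

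Assumptions, none of them from the SAP: p_s = 80%; s from 0.87 down to 0.60; g of 5, 10 or 20 points; 1:1 allocation in Step 2. The pregnancy side is taken as the full 115 women. The postpartum side has s × 115/2 women per vaccine, so at most about 57. The standard error is the Wald form, √[p₁(1 − p₁)/n₁ + p₂(1 − p₂)/n₂].

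| s | n pregnancy / postpartum | Spurious difference, g = 5 / 10 / 20 points | 95% CI half-width |
|---|---|---|---|
| 0.87 | 115 / 50 | 0.6 / 1.3 / 2.6 | 13.3 to 13.5 |
| 0.80 | 115 / 46 | 1.0 / 2.0 / 4.0 | 13.7 to 13.9 |
| 0.70 | 115 / 40 | 1.5 / 3.0 / 6.0 | 14.5 to 14.7 |
| 0.60 | 115 / 34 | 2.0 / 4.0 / 8.0 | 15.3 to 15.7 |

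Example, s = 0.60 and g = 20: the pregnancy side is 0.60 × 80 + 0.40 × 60 = 72%, the postpartum side 80%, a difference of 8 points. If non-entrants respond better, the sign reverses.

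Were the two proportions tested at the two-sided 5% level, the chance of a nominally significant result with no timing effect would run from 5.1% (s = 0.87, g = 5) to 17% (s = 0.60, g = 20).

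**Precision after restricting Arms 1A/1B to s × 115 women, both sides at 80%.**

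| s | n pregnancy / postpartum | Half-width, restricted | Half-width, unrestricted |
|---|---|---|---|
| 0.87 | 100 / 50 | 13.6 | 13.3 to 13.5 |
| 0.80 | 92 / 46 | 14.2 | 13.7 to 13.9 |
| 0.70 | 80 / 40 | 15.1 | 14.5 to 14.7 |
| 0.60 | 69 / 34 | 16.3 | 15.3 to 15.7 |

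The interval widens by about 0.1 to 0.6 points for s from 0.87 to 0.70, and by up to 1.0 point at s = 0.60.

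**The case against.** The strongest reply is that item iv is a descriptive secondary table. It asks for proportions with intervals and names no test, and using vaccinated women follows the SAP's general as-treated approach. Bias arises only if Step 2 entry is related to response, and the SAP has no data on that. This limits the weight of the point, but item iv remains the only answer to an objective worded as a comparison.

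Several stronger readings are tempting and are not supported:

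- *All Step 1 vaccinees are used.* They are not. Early deliveries are excluded, and a woman lost before week 4 has no outcome, so only losses after week 4 separate the two sides. The 13% implied by 345 and 300 is therefore a loose anchor. It may include earlier losses, and it does not count Step 2 screening or new pregnancy.
- *Timing is confounded with retention as a matter of fact, and the postpartum response will look better.* The SAP supports neither. Nothing in it shows that newly pregnant women or screening failures respond worse.
- *The bias is large.* Taking 35% not entering with a 30-point gap gives 0.35 × 0.30 = 10.5 points, but that needs two extreme assumptions and still lies inside the interval half-width. The small Step 2 arms widen the interval; they do not enlarge the bias.
- *A restricted comparison would be fully like for like.* It conditions on events after active vaccine or placebo, and the other Step 2 criteria are not in the SAP. Nor does the SAP say that new pregnancy is recorded in Arms 1A/1B at 24 weeks.

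The early-delivery sentence can be read as covering both sides, in which case only its wording needs attention. The protocol and the Analysis Implementation Plan are not at hand and may define the subsets. The SAP describes the latter as table outlines and coding descriptions, however, while item iv itself states the comparison and its sole exclusion.

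**Conclusion.** The concern holds in a limited form. Item iv applies completion of Step 1, Step 2 screening and absence of new pregnancy to the postpartum side only, and no stated restriction, adjustment or sensitivity analysis offsets this. The comparison can be biased in either direction if retention or new pregnancy is related to antibody response.

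Under the assumptions above the spurious difference is about 0.6 to 8 points, small to moderate against a half-width of about 13 to 16 points. The case for acting rests on the low cost of a partial remedy from follow-up that the SAP already plans, and not on any demonstrated error in the result.

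**What to change.** In section 5.4, item iv:

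1. Add a comparison that restricts Arms 1A and 1B to women who completed the Step 1 visit at 24 weeks after delivery and, where this is recorded, were not newly pregnant at it. Report it beside the unrestricted figures. If new pregnancy was not recorded in these arms, apply the completion condition alone and say so.
2. State that the exclusion for delivery before week 4 of Step 1 applies to Arm 1C women entering Step 2 as well as to Arms 1A and 1B.
3. Record two limitations: comparability assumes that vaccine versus placebo does not affect completion or new pregnancy, and other Step 2 screening criteria may remain unmatched.

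The cost is a few lines of SAP text and a subset flag for attendance at a visit that item iii already uses. This comparison will have somewhat fewer Step 1 women and a slightly wider interval.
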